## 3.4 CCI [REDACTED]

CCI [REDACTED]

### 3.4.1 CCI [REDACTED]

CCI [REDACTED]

CCI [REDACTED]

CCI [REDACTED]

CCI [REDACTED]

CCI [REDACTED]

- CCI [REDACTED]
- CCI [REDACTED]
- CCI [REDACTED]
- CCI [REDACTED]
- CCI [REDACTED]

CCI [REDACTED]

- CCI [REDACTED]
- CCI [REDACTED]
- CCI [REDACTED]
- CCI [REDACTED]

### 3.4.1.1 CCI [REDACTED]

CCI [REDACTED]

- CCI [REDACTED]
- CCI [REDACTED]
- CCI [REDACTED]
- CCI [REDACTED]
- CCI [REDACTED]

CCI [REDACTED]

- CCI [REDACTED]

CCI [REDACTED]

[figure not shown]
CCI [REDACTED]

CCI [REDACTED]

**Table 6** CCI

The diagram consists of four rectangular blocks arranged horizontally. Each block is black with the text 'CCI' in white. The first three blocks are of equal size and are positioned side-by-side. The fourth block is also black and white, but it is significantly taller than the others, extending from the top line down to the bottom line. Below this fourth block, the word 'CCI' is written in a smaller, black, sans-serif font.

[figure not shown]
CCI

CCI

[figure not shown]
CCI

[figure not shown]
• CCI

• CCI

[figure not shown]
CCI

CCI

CCI

3.4.1.2 CCI

CCI

[figure not shown]
CCI

CCI

CCI

[figure not shown]

3.4.2

[figure not shown]
CCI

[figure not shown]
CCI

[figure not shown]
CCI

[figure not shown]
CCI

CCI

CCI

3.4.3

[figure not shown]
CCI

CCI

CCI

CCI

CCI

## 3.5 Other Variables

### 3.5.1 Baseline Characteristics

Baseline characteristics that will be collected or derived are:

- Demographics: age (years), sex, race and ethnicity.
- Patient characteristics: weight (Kg), height (cm), body mass index (BMI kg/m^2).
- Medical history: name of past and/or concomitant diseases (verbatim and coded using the latest or current version of the MedDRA dictionary), start and stop dates.
- Nicotine use: smoking status (current, former, never) and pack years.
- Characteristics of NSCLC at diagnosis: original diagnosis date, primary tumor location, histology type, TNM classification, American Joint Committee on Cancer (AJCC) staging.
- Extent of disease at entry of study: current AJCC staging, evidence of disease (yes/no), sites of locally advanced disease, recent progression (yes/no, date).
- Previous disease-related radiotherapy: Total dose, Radiotherapy treated location, Time from completion of radiotherapy to study treatment, Dose per fraction, Number of fraction doses, frequency of fraction doses per day, concomitant chemoradiotherapy, treatment setting, radiotherapy technique.
- Previous disease-related cancer therapy: Number of chemotherapy regimens, number of cycles, best response to previous chemoradiotherapy, therapy class, treatment status.
- Relevant surgical history: surgical procedure (verbatim and coded using the latest or current version of the MedDRA dictionary) and date of surgery.

### 3.5.2 Prior and Concomitant Medications and Therapies

All therapies (drug or non-drug), including herbal preparations, whether prescribed or over-the-counter, that are used during the study will be recorded in the eCRF. Details include generic and/or brand names of medications, WHO drug dictionary encoding, reason for use, route, dose, dosing frequency, and start and stop dates.

Prior therapies are defined as those with at least one dose/treatment taken before the date of the first dose of study medication.

Concomitant therapies are defined as those with at least one dose/treatment taken between the date of first dose (inclusive) and the date of last dose (inclusive) of durvalumab.

[figure not shown]
Missing start and stop dates for medications will be imputed using the rules described in Section 4.1.3.

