6.4 Concomitant therapy

The Investigator must be informed as soon as possible about any medication taken from the time of screening until the end of the clinical treatment phase of the study including the follow-up period following the last dose of study drug.

Any medication or vaccine including over-the-counter or prescription medicines, vitamins, and/or herbal supplements that the patient is receiving at the time of enrollment or receives during the study must be recorded along with:

- Reason for use
- Dates of administration including start and end dates
- Dosage information including dose, unit, and frequency

Patients must be instructed not to take any medications, including over-the-counter products, without first consulting with the Investigator.

Restricted, prohibited, and permitted concomitant medications are described in [Table 6](#) and [Table 7](#). Refer also to the Dosing Modification and Toxicity Management Guidelines (see Section [8.4.5.1](#)).

Table 6 Prohibited concomitant medications

Prohibited medication/class of drug:	Usage:
Any investigational anticancer therapy other than those under investigation in this study	Should not be given concomitantly while the patient is on-study treatment.
mAbs against CTLA-4, PD-1, or PD-L1 other than those under investigation in this study	Should not be given concomitantly while the patient is on-study treatment.
Any concurrent chemotherapy, radiotherapy, immunotherapy, or biologic or hormonal therapy for cancer treatment other than those under investigation in this study	Should not be given concomitantly while the patient is on-study treatment. (Concurrent use of hormones for noncancer-related conditions [eg, insulin for diabetes and hormone replacement therapy] is acceptable. Local treatment of isolated lesions, excluding TLs, for palliative intent is acceptable [eg, by local surgery or radiotherapy]).
Live attenuated vaccines	Should not be given through 30 days after the last dose of durvalumab.

Prohibited medication/class of drug:	Usage:

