9.4 Outcome measures for analyses

- 1 **AE:** Number and proportion of patients with AEs in total and by causality and severity
- 2 **AE:** Number and proportion of patients with Grade 3 and Grade 4 AEs in total and by causality
- 3 **SAE:** Number and proportion of patients with SAEs in total and by causality and severity
- 4 **AEs leading to death:** Number and proportion of patients with AEs leading to death
- 5 **AEs leading to treatment interruption or discontinuation:** Number and proportion of patients with AEs leading to treatment interruption and/or discontinuation
- 6 **AESI:** Defined as an AE of scientific and medical interest specific to understanding of the IP. AESIs for durvalumab include, but are not limited to, events with a potential inflammatory or immune-mediated mechanism and which may require more frequent monitoring and/or interventions such as steroids, immunosuppressants, and/or hormone replacement therapy. In order to further characterize safety objectives related to AESIs, outcome measures will be assessed, which may include (and are not necessarily limited to) the following:
 - (a) Number and proportion of patients with AESIs, by predefined type (or newly defined by this study) in total and by seriousness, severity and causality, including immune-relatedness;

- (b) Number and proportion of patients who received steroids, immunosuppressants, and/or hormone replacement therapy to manage AESIs;
- (c) Time from start of durvalumab to the onset of an AESI predefined type, all interventions of AESIs by type of intervention (including intervention with steroids, immunosuppressants, and/or hormone replacement therapy), and time from onset of an AESI type to resolution;
- (d) Duration of the intervention with steroids, immunosuppressants, and/or hormone replacement therapy until the resolution of AESI;
- (e) The imAEs will be assessed as a subset of AESIs. An imAE is defined as an AESI that is associated with drug exposure and is consistent with an immune-mediated MOA and where there is no clear alternate etiology.
- (f) Laboratory findings, vital signs, and other safety parameters associated with AESIs will be summarized as part of the AESI outcome measures.

7 **PFS:** Defined as the time from the first date of treatment until the date of objective disease progression or death (by any cause in the absence of progression) regardless of whether the patient withdraws from IP or receives another anticancer therapy prior to progression.

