### **3.2.3 Adverse Events**

AEs and SAEs will be collected throughout the study, from time of the patient signing the informed consent and 90 days after the last dose of durvalumab. A treatment emergent adverse event (TEAE) is an AE with an onset date or a pre-existing AE worsening following the first dose of study treatment through to 90 days after the last dose of durvalumab.

The Medical Dictionary for Regulatory Activities (MedDRA) (using the latest or current MedDRA version) will be used to code the AEs. AEs will be graded according to the National Cancer Institute Common Terminology Criteria for AEs (CTCAE Version 5.0). The meaning of these categories are as follows:

- Grade 1: Mild AE
- Grade 2: Moderate AE
- Grade 3: Severe AE
- Grade 4: Life-threatening or disabling AE
- Grade 5: Death related to AE

Any TEAE will be included in the AE summaries as detailed in Section 4.5.1.

Missing start and stop dates for AEs will be imputed using the rules described in Section 4.1.3.

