### **4.5 Analysis of Secondary Safety Endpoints**

#### **4.5.1 Adverse Events**

All TEAEs reported up until 90 days following completion or discontinuation of durvalumab treatment or until the initiation of the first subsequent therapy (whichever occurs first) will be included in the summaries unless explicitly stated otherwise below.

All TEAEs will be summarised descriptively, in terms of number of patients (n) and percentage of patients (%) reporting the event by MedDRA SOC and PT.

Listings of AEs will include the date of onset, date of resolution (if AE is resolved) and investigator's assessment of severity, relationship to durvalumab, and NCI CTCAE Grade. Separate listings will be produced for all AEs, PRAEs, SAEs, AESIs, AEPIs, imAEs, AEs with outcome of death, AEs leading to discontinuation of durvalumab, AEs leading to discontinuation of study. Listings of AESIs, AEPIs and imAEs will also include the additional information (eg, intervention, dose, duration of therapy etc.) recorded for these AEs. All AEs that are not treatment-emergent will be flagged in the data listings and the time of onset will be flagged as 'pre-treatment', 'post-treatment and no other anti-cancer therapy' and 'after initiation of other anti-cancer therapy'.

An overall summary of AE data will be presented including the number and percentage of patients reporting the following:

- At least one AE
- At least one PRAE
- At least one AE of CTCAE Grade 3 or Grade 4
- At least one PRAE of CTCAE Grade 3 or Grade 4
- At least one SAE
- At least one Serious PRAE
- At least one AE leading to discontinuation of study treatment

- At least one PRAE leading to discontinuation of study treatment
- At least one AE leading to treatment interruption
- At least one PRAE leading to treatment interruption
- At least one AE with outcome of death
- At least one PRAE with outcome of death
- At least one AESI
- At least one AEPI
- At least one PRAE of special interest (AESI)
- At least one PRAE of possible interest (AEPI)
- At least one imAE
- At least one immune-mediated PRAE

The following summaries including the number and percent of patients by SOC and PT will be presented separately:

- All AEs / PRAEs
- All AEs / PRAEs of CTCAE Grade 3 or Grade 4
- All PRAEs of CTCAE Grade 3 or Grade 4 occurring within the six months of first dosed date
- All PRAEs which start within 90 days of last dose of durvalumab (irrespective of start of subsequent anti-cancer therapy)
- All AEs

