#### 4.5.1.1 Adverse Events of Special Interest and Possible Interest

Preferred terms used to identify adverse events of special interest and possible interest (as defined in 3.2.3) will be listed before DBL and documented in the Study Master File. Grouped summary tables of certain MedDRA preferred terms will be produced and may also show the individual preferred terms which constitute each AESI/AEPI grouping. Groupings will be based on preferred terms provided by the medical team prior to DBL, and a listing of the preferred terms in each grouping will be provided.

Summaries of the above-mentioned grouped AE categories will include number (%) of patients who have:

- Any AESI/AEPI
- Any AESI/AEPI by SOC, PT and maximum CTCAE grade
- Any AESI/AEPI of maximum CTCAE grade 3 or 4
- Any serious AESI/AEPI
- Any AESI/AEPI with outcome of death
- Any AESI/AEPI possibly related to study treatment
- Any AESI/AEPI leading to concomitant medication use (steroids)
- Any AESI/AEPI leading to concomitant medication use (high dose steroids)
- Any AESI/AEPI leading to concomitant medication use (endocrine therapy)
- Any AESI/AEPI leading to concomitant medication use (other immunosuppressants)
- At least one AESI/AEPI leading to discontinuation of study treatment
- Possibly related AESI/AEPI leading to discontinuation of study treatment
- Time to onset of first AESI/AEPI (days)
- Duration (days) of AESI/AEPI

An overall AESI/AEPI summary will be presented, including number and percentage of patients in each of these categories. Any AESI/AEPI presented by outcome will also be provided.

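### Read with the SAP's definition of concomitant therapy, the AESI/AEPI and imAE treatment-use rows omit steroids, immunosuppressants or endocrine therapy first started after the last infusion, although the events are counted for 90 days more.

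*SAP*

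**What the plan says.** SAP 3.5.2 holds the SAP's only definition of concomitant therapy: at least one dose or treatment "taken between the date of first dose (inclusive) and the date of last dose (inclusive) of durvalumab". It has no extension into follow-up and no separate class for therapy started after the last dose.

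The event window is longer. SAP 3.2.3 defines a treatment-emergent event as one that starts or worsens "following the first dose of study treatment through to 90 days after the last dose of durvalumab". SAP 4.5.1 puts into the summaries "All TEAEs reported up until 90 days following completion or discontinuation of durvalumab treatment or until the initiation of the first subsequent therapy", whichever comes first.

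SAP 4.5.1.1 then lists rows for the AESI/AEPI tables. One begins "Any AESI/AEPI leading to concomitant medication use (steroids". Parallel rows cover high dose steroids, endocrine therapy and other immunosuppressants. SAP 4.5.1.2 says that imAEs are summarised in a similar way.

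On the protocol side, Section 6.4 asks for medication to be reported from screening "until the end of the clinical treatment phase of the study including the follow-up period following the last dose of study drug". Table 2 schedules concomitant medication at 30 days, 2 months and 3 months after the last dose. Among the AESI measures that Section 9.4 says may be assessed is the "Number and proportion of patients who received steroids, immunosuppressants, and/or hormone replacement therapy to manage AESIs", with no limit at the last dose.

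**The concern.** Two parts of one table row run on different clocks. The event can be counted up to 90 days after the last infusion. The treatment given for it is concomitant, by the SAP's definition, only if at least one dose was taken by the day of the last infusion.

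Dosing is every 28 days, so toxicity often appears between infusions. If dosing later resumes, a steroid started in that gap precedes the last dose and is counted. If the same toxicity ends treatment, the infusion before it becomes the last dose, and a steroid started the next day is outside the definition. Whether treatment is counted can therefore depend on whether the event stopped durvalumab. For example, a patient with one infusion who develops pneumonitis on Day 15 and starts steroids that day has an AESI in the table but no concomitant steroid use.

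At stake is the description of how much immunosuppression and hormone replacement durvalumab toxicity required. For a study whose aim is safety and tolerability, that is a useful secondary result, and under this reading it can only be understated.

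**Working it through.** The plan states no figure for this point that could be reproduced. The check compares windows by date arithmetic.

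**Inputs**
- Cycle length: 28 days (SAP 1.2.1; Protocol 1.1).
- Maximum doses: 13 (Protocol 6.1.2.1; SAP 1.2.1).
- End of concomitant-therapy window: day of last dose (SAP 3.5.2).
- End of event window: last dose + 90 days, unless subsequent therapy starts earlier (SAP 3.2.3 and 4.5.1).

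**Formulas**, for a patient with k on-schedule doses
- Day of last dose: L = 1 + 28 × (k − 1).
- End of event window: T = L + 90.
- Uncovered share: 90 / T.

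| Doses k | Last dose day L | Event window end T | Uncovered share 90/T |
|---|---|---|---|
| 1 | 1 | 91 | 90/91 = 98.9% |
| 2 | 29 | 119 | 90/119 = 75.6% |
| 3 | 57 | 147 | 90/147 = 61.2% |
| 6 | 141 | 231 | 90/231 = 39.0% |
| 13 | 337 | 427 | 90/427 = 21.1% |

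These are shares of days, not of events, and 90 days is a maximum because the summaries stop at the first subsequent therapy. With the event window used for both, the uncovered period is 0 days in every line.

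**How many patients?** Protocol 2.3.2.1 reports that approximately 10% of patients in durvalumab monotherapy studies stopped because of an AE. Applied to the planned 102, 0.10 × 102 ≈ 10 patients. That is a ceiling for the group whose treatment is ended by toxicity, and only if the rate carries over. To be missed, such a patient's event must also be an AESI, AEPI or imAE, be treated with one of the listed classes, and have that class first started after the last infusion. The documents give none of these fractions. Nor do they give a figure for patients who complete treatment or stop for another reason and then have a treated event during follow-up.

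**Illustration only; both inputs are assumed.** Suppose 20 of 102 patients (19.6%) have a steroid-treated AESI. If 10%, 25% or 50% of them first receive the steroid after the last dose, the row shows 18/102 = 17.6%, 15/102 = 14.7% or 10/102 = 9.8%.

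**The case against.** The strongest reply is that SAP 4.5.1.1 does not cite 3.5.2. The output that plainly uses that definition is the general medication summary in SAP 4.2.4, where an on-treatment window is a common convention. The rows in 4.5.1.1 are worded by event, and event-level data exist: Protocol 8.3.4 collects whether treatment was given for each AE, SAP 3.5.2 records the reason for use of each therapy, and SAP 4.5.1 promises listings with intervention details. A programmer could build the rows correctly from these. The protocol also applies the term concomitant medication to follow-up visits in Table 2.

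This stands in part. The link rests on a shared term, not a cross-reference, so the understatement follows from reading the SAP by its own definition and is not certain to happen. But the SAP names no other source or window for these rows, and the AE treatment field is not described as recording drug class or dose, which the rows need. The listings do not replace a number and proportion. It is also fair that Protocol 9.4 offers its AESI measures as ones that may be included, so this is not a mandatory outcome.

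A reader might infer that the rule removes the most severe cases from the safety tables. It does not. The same events still count as AESIs, by grade, as serious or fatal, and as leading to discontinuation. imAEs are those identified by the investigator (SAP 3.2.3.3), so their number does not depend on 3.5.2. A reader might also infer that one radiotherapy cohort is affected more. That would need the cohorts to differ in when treatment stops, and the documents do not show this.

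**Conclusion.** The windows do not match, and the point should be corrected. Under the SAP's own definition, the treatment-use rows for AESIs, AEPIs and imAEs leave out any steroid, immunosuppressant or endocrine therapy first started after the final infusion, while the event itself is counted for up to 90 days more. The error can only lower the reported use. Relative to the event window, the gap is widest in patients who stop early: up to 98.9% of the window after one dose, against 21.1% after 13.

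The scope is narrow. AE, AESI and imAE incidences, the primary endpoint and the listings are unchanged, and therapy begun on or before the last dose and continued is still counted. It would be tempting to say that about 10 patients will be lost. The documents support that figure only as a conditional ceiling for toxicity-related stopping, borrowed from other studies; the actual number cannot be derived.

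The conclusion assumes that the term in 4.5.1.1 carries its 3.5.2 meaning. The window shares assume on-schedule dosing and no earlier subsequent therapy.

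**What to change.** In SAP 4.5.1.1 and 4.5.1.2, state that the treatment-use rows count any steroid, immunosuppressant or endocrine therapy whose recorded reason for use is the AESI, AEPI or imAE, and which started between the first dose and the earlier of 90 days after the last dose and the start of subsequent anticancer therapy. Add that this applies irrespective of the definition in 3.5.2. The general concomitant-medication summary in SAP 4.2.4 may keep its on-treatment window, so 3.5.2 itself need not change.

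The cost is SAP wording and a programming change. The protocol already collects the medication data to 3 months after the last dose, and the reason for use is recorded. The downside for the sponsor is that reported use of immunosuppression may rise.

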### 3.5.3

CCI

CCI

CCI

## 4. ANALYSIS METHODS

### 4.1 General Principles

#### 4.1.1 General Statistical Considerations

The following general statistical considerations will be applied for the analyses and presentation of the data. In case of any specific deviations, methods will be specifically noted on the relevant output.

- All data, demography, baseline characteristics, safety, efficacy and biomarkers, will be summarized using descriptive statistics, as appropriate for the type of data, for the SAF. In addition, all efficacy and safety data and some selected relevant data (eg, patient disposition, demography and baseline characteristics) will be summarised separately for each cohort (standard radiotherapy and palliative radiotherapy) and overall.
- Continuous variables will be summarized by the number of observations (n), mean, standard deviation, median, minimum, and maximum.
- For the continuous data, the summary statistics will be displayed with the following accuracy (number of dps):
  - The minimum and maximum with same accuracy as the raw data.
  - The mean and median will be rounded to 1 additional dp more than the number of dps in the raw data.
  - The standard deviation will be rounded to 2 additional dps more than the number of dps in the raw data.
  - If the number of observations is 1, the SD will not be derived.
- Categorical variables will be summarized by frequency counts and percentages for each category and percentages will be rounded to one dp.
- As a default, percentages will be calculated using the number of patients who have non-missing data as the denominator. Therefore, percentages for missing data will not be presented in the results. If the denominator is different from this default, it will be explained in a footnote to the output.
- SAS® version 9.4 or higher will be used for all analyses.
- Exact CIs for proportions will be calculated using the Clopper-Pearson method.

- For percentiles of survival times based on the Kaplan-Meier method (eg, median survival), CIs will be calculated using the default method available in the SAS LIFETEST procedure (ie, the Klein and Moeschberger extension of the Brookmeyer-Crowley method).
- For point-estimates of survival based on the Kaplan-Meier method (eg, for PFS12), CIs will be calculated using the default method available in the SAS LIFETEST procedure (ie, using Greenwood's estimate of standard error and a log-log transformation).
- The data will be included in summaries/analyses using the following criteria:
  - All laboratory data, vital signs and ECG data that are recorded at unscheduled visits will be included in the summaries using the visit windows defined in Section 4.1.4.1.
  - The tumor measurements and PRO data should not be affected by any delays in treatment cycles/dates of start of treatment cycles as it is intended that they are only recorded at pre-scheduled time points. These data will be included in the summaries and analyses of the data using the visit windows defined in Section 4.1.4.2.
- All data collected including scheduled, delayed and unscheduled data will be listed in the patient data listings which are produced for all treated patients. They will be ordered by treatment/not treated, centre, radiotherapy group, patient and visit and, if relevant, timepoint when they were recorded. Patients who are included in the SAF will be flagged. Depending on the availability of the data, all data for the patients who are not treated will be listed separately. They will be ordered by centre, radiotherapy group, patient and visit and timepoint, if relevant.
- All adverse events will be coded using MedDRA and NCI CTCAE Grade and will be reported using SOC and PT, and NCI CTCAE Grade, as appropriate.
- All concomitant and previous medications will be coded using WHO drug dictionary and will be reported using anatomical therapeutic chemical (ATC) classification and generic term.
- Baseline is defined as the last assessment of the variable under consideration prior to the first dose of durvalumab regardless of whether the assessment is on Day 1, Screening or unscheduled.
- Patients who failed the screening in the first instance but later rescreened and passed the screening will be part of summary tables along with other patients who passed the screening in the first instance.
- Patients who failed both first screening and rescreening will not be part of summary tables but a listing will be generated for these patients.
- Participants affected by the COVID-19 pandemic will be listed including category for study disruption due to the pandemic and details of disruption. The study disruptions due to the pandemic will also be summarized. Subject disposition will be summarized including number (%) of patients who discontinued treatment due to the pandemic and who withdrew from study due to pandemic. Important protocol deviations will be summarized including number (%) of patients with at least one important protocol

deviation related to the pandemic. Number and percentage of patients with confirmed/suspected COVID-19 infection along with demographic characteristics, medical history and adverse event of patients with confirmed/suspected COVID-19 infection will be presented. If the study has fewer than 5 and/or less than 2% of the patient population with confirmed/suspected COVID-19 infection, then a listing will be presented instead of summary.

